Neurological worsening	Neurological worsening may occur due to disease progression or Cu mobilization	Dose modification (Section 6.6) or discontinuation (Section 7)

Abbreviations: ALT = alanine aminotransferase; AST = aspartate aminotransferase; BMI = body mass index; Cu = copper; IB = Investigator's Brochure; PT-INR = prothrombin time-international normalized ratio; WD = Wilson disease.

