
Investigators must document their review of each laboratory safety report.

10.3. Appendix 3: Adverse Events: Definitions and Procedures for Recording, Evaluating, Follow-up, and Reporting

Adverse Event Definition

- An AE is any untoward medical occurrence in a patient or clinical study patient, temporally associated with the use of study drug, whether or not considered related to the study drug.
- NOTE: An AE can therefore be any unfavorable and unintended sign (including an abnormal laboratory finding), symptom, or disease (new or exacerbated) temporally associated with the use of study drug.

Events Meeting the AE Definition

- Any abnormal laboratory test results (hematology, clinical chemistry, or urinalysis) or other safety assessments (eg, ECG, radiological scans, vital signs measurements), including those that worsen from baseline, considered clinically significant in the medical and scientific judgment of the Investigator (ie, not related to progression of underlying disease).
- Exacerbation of a chronic or intermittent pre-existing condition including either an increase in frequency and/or intensity of the condition.
- Signs, symptoms, or the clinical sequelae, regardless of whether a suspected drug-drug interaction.
- The signs, symptoms, and/or clinical sequelae resulting from lack of efficacy will be reported as AE or SAE if they fulfil the definition of an AE or SAE.
- Overdose per se will not be reported as an AE/SAE unless it is an intentional overdose taken with possible suicidal/self-harming intent. Such overdoses should be reported regardless of sequelae.
- Pre-existing conditions that are detected after administration of study drug with an onset date prior to administration should be considered medical history.

Events NOT Meeting the AE Definition

- Medical or surgical procedure (eg, endoscopy, appendectomy): the condition that leads to the procedure is the AE.
- Anticipated day-to-day fluctuations of pre-existing disease(s) or condition(s) present or detected at the start of the study that do not worsen.
- A medication error (including intentional misuse, abuse, and overdose of the product) or use other than what is defined in the protocol is not considered an AE unless there is an untoward medical occurrence as a result of a medication error.

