- Cases of pregnancy that occur during maternal or paternal exposure to investigational product are to be reported within 24 hours of Investigator/site awareness. Data on fetal outcome and breastfeeding will be collected for regulatory reporting and safety evaluation.
- Any clinically significant abnormal laboratory findings or other abnormal safety assessments which are associated with the underlying disease, unless judged by the Investigator to be more severe than expected for the patient's condition.
- Situations in which an untoward medical occurrence did not occur (social and/or convenience admission to a hospital).

Serious Adverse Event Definition

If an event is not an AE per definition above, then it cannot be an SAE even if serious conditions are met (eg, hospitalization for signs/symptoms of the disease under study, death due to progression of disease).

An SAE is defined as an AE that, at any dose:
1. Results in death
2. Is life-threatening The term 'life-threatening' in the definition of 'serious' refers to an event in which the patient was at risk of death at the time of the event. It does not refer to an event, which hypothetically might have caused death, if it were more severe.
3. Requires inpatient hospitalization or prolongation of existing hospitalization In general, hospitalization signifies that the patient has been detained (usually involving at least an overnight stay) at the hospital or emergency ward for observation and/or treatment that would not have been appropriate in the physician's office or outpatient setting. Complications that occur during hospitalization are AEs. If a complication prolongs hospitalization or fulfills any other serious criteria, the event is serious. When in doubt as to whether "hospitalization" occurred or was necessary, the AE should be considered serious. Hospitalization for elective treatment of a pre-existing condition that did not worsen from baseline is not considered an AE.
4. Results in persistent disability/incapacity 
 • The term disability means a substantial disruption of a person's ability to conduct normal life functions. • This definition is not intended to include experiences of relatively minor medical significance such as uncomplicated headache, nausea, vomiting, diarrhea, influenza, and accidental trauma (eg, sprained ankle) which may interfere with or prevent everyday life functions but do not constitute a substantial disruption.

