7.3.2.1. Overall Summary of Adverse Events

An overall summary of TEAEs will be presented, including the number of events and the number and percentage of patients experiencing AEs. Percentage will be calculated as $n / N \times 100$, where n is the number of patients with events and N is the number of patients in the Safety Analysis Set. The summary will include categories indicating how many events are TEAEs, treatment-emergent SAEs, and treatment-emergent non-SAEs.

A patient-level listing of all TEAEs will be presented. Separate listings will be produced for SAEs, AEs leading to study drug withdrawal, AEs resulting in death, AEs leading to withdrawal from the study, and pre-treatment AEs (PTAEs).

7.3.2.2. Adverse Events and Serious Adverse Events by System Organ Class and Preferred Term

The number of TEAEs and the number and percentage of patients with events will be presented by SOC and PT. Patients are counted once in each SOC and PT. Percentages will be based on the Safety Analysis Set. The SOCs will be listed in descending frequency as will PTs' within each SOC. If needed, PTs will also be ordered alphabetically.

Treatment-emergent SAEs, treatment-emergent non-SAEs, TEAEs leading to withdrawal of study drug, TEAEs leading to death, and PTAEs will be summarized using the same approach.

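### Two examples in the Appendix 3 SAE definition conflict with the AE definition they rely on, so sites may classify serious worsening of Wilson disease inconsistently

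*Protocol*

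**What the plan says.** **The rule.** The Serious Adverse Event Definition in Protocol Section 10.3 (Appendix 3) opens with a condition: "If an event is not an AE per definition above, then it cannot be an SAE even if serious conditions are met". Its examples of events removed in this way are "hospitalization for signs/symptoms of the disease under study, death due to progression of disease".

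**The definition it relies on.** Earlier in the same appendix, an AE is any untoward occurrence during use of study drug, related or not. It includes an unfavorable sign, "symptom, or disease (new or exacerbated) temporally associated with the use of study drug". The list of events that meet the definition includes:
- "Exacerbation of a chronic or intermittent pre-existing condition including either an increase in frequency and/or intensity of the condition"
- "The signs, symptoms, and/or clinical sequelae resulting from lack of efficacy will be reported as AE or SAE if they fulfil the definition"

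**Overlap of disease and drug effect.** Table 3 in Protocol 2.3.1 states: "Neurological worsening may occur due to disease progression or Cu mobilization".

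**Outputs.** Protocol 9.4.2 tabulates AEs, SAEs and AEs leading to death. SAP 7.3.2.1 plans: "Separate listings will be produced for SAEs, AEs leading to study drug withdrawal, AEs resulting in death". SAP 7.3.2.2 summarizes treatment-emergent SAEs and treatment-emergent AEs leading to death. Neither document specifies a table or listing of deaths from any cause.

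**The concern.** The examples ask the investigator to decide whether an event is disease or drug before deciding whether to report it. In this trial that decision is hard. The protocol itself gives disease progression and copper mobilization as alternative causes of the same neurological picture. For hepatic events the overlap is an inference, though a reasonable one: transaminase elevation is a listed drug risk in Table 3, and Protocol 2.2.1 says that deaths in inadequately treated Wilson disease usually follow from cirrhosis.

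The design adds to the difficulty. Standard of care stops before Day 1 (Protocol 6.5), and Protocol 4.2 describes a risk of rapid progression to liver failure in patients who discontinue treatment for Wilson disease. Loss of disease control on the new drug could therefore be recorded as progression.

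At stake are consistent SAE classification across sites, the 24-hour SAE reporting route in Protocol 8.3.1, and the completeness of the SAE and death tables. An event that was never entered as an AE may be hard to recover at analysis.

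**Working it through.** The point concerns definitions, and the plan states no figure to reproduce. The check sets the texts side by side.

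**Step 1: does the AE definition remove the two examples?** The list of events not meeting the AE definition in Appendix 3 covers:
- procedures, where the underlying condition is the event;
- expected fluctuation of existing disease, but only without worsening;
- medication errors without an untoward consequence;
- pregnancy, which has its own reporting route;
- abnormal laboratory or other safety-assessment findings associated with the underlying disease, unless judged more severe than expected;
- situations with no untoward occurrence, such as a social admission.

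Hospital admission for worsening Wilson disease is not on this list, and neither is death from progression. The only carve-outs for the underlying disease concern non-worsening fluctuation and laboratory or other assessment findings.

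**Step 2: does the AE definition include them?** Yes, for worsening disease. Exacerbated disease is in the definition, exacerbation of a pre-existing condition is on the list of qualifying events, and the consequences of lack of efficacy qualify if the definition is met. The hospitalization criterion points the same way: it sets aside elective treatment only for a condition that has not worsened since baseline.

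**Step 3: compare.** By the definition, serious worsening of Wilson disease is an AE and, if a seriousness criterion is met, an SAE. By the examples, it is not an AE and so cannot be an SAE. Both cannot apply to the same event.

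**Step 4: follow an event left out under the examples.** It is not an AE record. It is therefore absent from the SAE and death tabulations in Protocol 9.4.2 and from the SAE and death summaries and listings in SAP 7.3.2.1 and 7.3.2.2, all of which start from AEs.

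**Step 5: illustration of scale only.** Assume that all of the approximately 28 planned patients are dosed and form the Safety Analysis Set.

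| Events in the table | Rate | Exact two-sided 95% interval |
|---|---|---|
| 1 of 28 | 1/28 = 3.6% | 0.1% to 18.3% |
| 0 of 28, if that one event is left out | 0% | 0% to 12.3% |

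The one-sided 95% upper limit for 0 of 28 is 1 − 0.05^(1/28) = 10.1%. These figures hold for any event in any study of 28 patients. They show how much one record weighs, not how many would be lost.

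**The case against.** The strongest reply is that the rule is conditional. It removes only events that are not AEs under the definition above it, and that definition includes worsening disease. A site that applies the definition reports the event. A reader might infer from the examples that the protocol bars disease-related hospitalizations and deaths from being SAEs. The documents do not support that: the operative definition points the other way, and the defect is a contradiction that sites may resolve differently.

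Other text also limits the harm:
- Protocol 7.1 asks for any new clinically relevant finding to be reported as an AE.
- Table 6 in Protocol 6.6 calls for a neurologic event of special interest to be reported when the UWDRS-III score rises by a set amount and the Investigator considers the rise clinically significant. Protocol 8.3.6 says that no such events are defined, so the two places disagree on the label, but the instruction to report remains.
- The causality assessment in Appendix 3 already weighs progression of the disease state and underlying disease.
- SAP 5.2 treats deaths as SAEs and collects them on a separate CRF. Protocol 7.2 names death as a reason for discontinuation, and SAP 7.1.1 summarizes and lists those reasons.
- Laboratory shift tables, CTCAE grading and eDISH plots (SAP 7.3.3.1 and 7.3.3.2), MELD and modified Nazer scores (SAP 7.2.4) and the Hepatic Adjudication Panel (Protocol 9.6) cover liver findings whatever their AE status.

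A reader might also infer that the main harms in general could drop out. That is too broad. Table 3 attributes anemia and leukopenia to copper depletion, so they are less exposed, and its hepatic entry is transaminase elevation that is generally mild to moderate. Nor does the single-arm design carry the point: a control arm under the same definition could have the same omissions.

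Most of this stands and narrows the point. What it does not do is return an omitted event to the SAE table or to the table of AEs leading to death. A disease-attributed hospitalization that does not end participation has no specified output of its own.

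**Conclusion.** The contradiction in Appendix 3 is real and worth correcting. The two examples conflict with the AE definition on which the rule depends. The likely consequence is inconsistent classification, with possible omission of serious neurological or hepatic worsening at sites that follow the examples. Certain or systematic loss of such events does not follow from the text.

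The number of events affected cannot be derived from the documents; the 3.6 points per event at 28 patients is only an illustration. The conclusion rests on three things: that some sites may be guided by the examples and not by the definition, that the AE-based outputs are the only SAE and death tables planned, and, for hepatic events, the inference that disease worsening and drug effect can present alike. The contents of the DMC and Hepatic Adjudication Panel charters and of the CRF are not in the documents, so any further protection there cannot be judged.

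**What to change.** 1. **Protocol Section 10.3, Appendix 3.** Reconcile the AE and SAE definitions by deleting or qualifying the two examples. Worsening of Wilson disease that meets a seriousness criterion should be recorded as an SAE, with attribution to disease or drug left to the existing causality assessment.
2. **SAP 7.3.2.** Add a listing of all deaths irrespective of attribution, drawn from the CRF that collects deaths and from the disposition data.

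A matching listing of all hospitalizations is not proposed. The documents describe no source for hospitalizations outside AE reporting, and Protocol 8.10 says that resource utilization is not evaluated, so it could need new data collection. Once the definition is reconciled, serious hospitalizations for worsening disease reach the SAE listing in any case.

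The cost is one sentence in the next amendment or a site letter, one additional SAP listing, and slightly more SAE reports. The change affects reporting only, not treatment.

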10.4. Appendix 4: Pregnancy Information

Definitions

Woman of Childbearing Potential (WOCBP)

A woman is considered fertile following menarche and until becoming post-menopausal unless permanently sterile (see below).

If fertility is unclear (e.g., amenorrhea in adolescents or athletes) and a menstrual cycle cannot be confirmed before first dose of study intervention, additional evaluation should be considered.

Women in the following categories are not considered WOCBP

1. Premenarchal
2. Premenopausal female with 1 of the following:
 - Documented hysterectomy
 - Documented bilateral salpingectomy
 - Documented bilateral oophorectomy
 - For individuals with documented permanent infertility due to an alternate medical cause other than the above, (e.g., mullerian agenesis, androgen insensitivity), Investigator discretion should be applied to determining study entry.
 - Note: Documentation can come from the site personnel's: review of the participant's medical records, medical examination, or medical history interview.
3. Postmenopausal female
 - A postmenopausal state is defined as no menses for 12 months without an alternative medical cause. A high follicle stimulating hormone (FSH) level in the postmenopausal range may be used to confirm a postmenopausal state in women not using hormonal contraception or hormonal replacement therapy. However, in the absence of 12 months of amenorrhea, a single FSH measurement is insufficient.

Contraception Guidance:

Guidance for Female Patients

Female patients of non-childbearing potential are exempt from contraception requirements.

Female patients of child-bearing potential must have a negative highly sensitive pregnancy test (urine or serum as required by local regulations) within 24 hours before the first dose of study drug.

The Investigator is responsible for the review of medical history, menstrual history, and recent sexual activity to decrease the risk for inclusion of a woman with an early undetected pregnancy.

Female patients of child-bearing potential must use a highly effective method of contraception, including at least one of the following, starting at least one menstrual cycle before first study drug administration and continuing for at least 30 days after the end of systemic exposure of the study drug, including at least one of the following:

- a. Intrauterine device (without Cu)
- b. Progestogen-only hormonal contraception (either oral, injectable, or implantable) associated with inhibition of ovulation
- c. Intrauterine progestogen releasing system
- d. Bilateral tubal occlusion
- e. Combined (estrogen and progestogen containing) hormonal contraception (either oral, intravaginal, or transdermal) associated with inhibition of ovulation. Estrogen-containing hormonal contraception is acceptable only if it has been used for at least 6 weeks immediately prior to the Day 1 visit. Estrogen-containing hormonal contraception may not be initiated during the study period.
- f. Surgical sterilization of the male partner (medical assessment of azoospermia is required if vasectomy was performed within the prior 6 months)

Sexual abstinence for female patients

Sexual abstinence is considered a highly effective method only if defined as refraining from heterosexual intercourse. In this study, abstinence is only acceptable if consistent with the patient's preferred and usual lifestyle. Abstinent female patients who wish to initiate a highly effective method of contraception during the study must refrain from heterosexual intercourse for at least 28 days.

Periodic abstinence (e.g. calendar, symptothermal, or post-ovulation methods) is not considered a highly effective method of contraception for female patients.

Other methods of contraception that are not considered highly effective for female patients

Barrier methods, such as male or female condoms, diaphragm, or cervical cap, used alone or in combination, are not acceptable.

Spermicides or spermicidal sponges, used alone or in combination with barrier methods, are not acceptable.

Withdrawal (coitus interruptus) is not acceptable.

Lactational amenorrhea is not acceptable.

Guidance for male patients with a partner who is a woman of childbearing potential

Male patients must use a condom and spermicide during heterosexual intercourse from the first dose of study intervention until at least 90 days after their final dose of study intervention.

Female partners of male patients who are of childbearing potential must use highly effective contraception as defined above, starting one menstrual cycle before (the male patient's) first study intervention administration and continuing until at least 90 days after the end of their male partner's systemic exposure to the study intervention.

Male patients must not donate sperm from the first dose of study intervention until at least 90 days after their final dose of study intervention.

Sexual abstinence for male patients

Sexual abstinence is considered a highly effective method only if defined as refraining from heterosexual intercourse. In this study, abstinence is only acceptable if consistent with the patient's preferred and usual lifestyle. Abstinent male patients who become heterosexually active with a WOCBP must use a condom and spermicide during intercourse.

Periodic abstinence (e.g. calendar, symptothermal, or post-ovulation methods for a female partner) is not considered a highly effective method of contraception for male patients.

Collection of Pregnancy Information

Pregnancy data will be collected during this study for all female patients and female partners of male patients. Exposure during pregnancy (also referred to as exposure *in utero*) can be the result of either maternal exposure or transmission of drug product via semen following paternal exposure. If a female patient becomes pregnant from the first dose of study drug up to 30 days after the end of systemic exposure or a male patient's female partner becomes pregnant from the first dose of study drug up to 90 days after the end of systemic exposure, the Investigator must submit the "Pregnancy/Breastfeeding Reporting and Outcome Form" to Alexion GDS via email or facsimile. When the outcome of the pregnancy becomes known, the form should be updated and submitted to Alexion GDS. If additional follow-up is required, the Investigator will be requested to provide the information.

Exposure of an infant to an Alexion product or other study drug during breastfeeding must also be reported (via the "Pregnancy/Breastfeeding Reporting and Outcome Form") and any AEs experienced by the infant must be reported to Alexion GDS or designee via email or facsimile.

Pregnancy in itself is not regarded as an AE unless there is a suspicion that the study drug may have interfered with the effectiveness of a contraceptive medication. However, complications of pregnancy and abnormal outcomes of pregnancy are AEs and may meet the criteria for an SAE (eg, ectopic pregnancy, spontaneous abortion, intrauterine fetal demise, neonatal death, or congenital anomaly). Elective abortions without complications should not be reported as AEs.

Any female patient who becomes pregnant while participating in the study will be discontinued from study drug and withdrawn from the study.

Male participants with partners who become pregnant

- The Investigator will attempt to collect pregnancy information on any male participant's female partner who becomes pregnant while the male participant is in this study. This applies to male participants who receive ALXN1840.
- After obtaining the necessary signed informed consent from the pregnant female partner directly, the Investigator will record pregnancy information on the appropriate "Pregnancy/Breastfeeding Reporting and Outcome Form" and submit it to Alexion within 24 hours of obtaining the consent. The female partner will also be followed to determine the outcome of the pregnancy. Information on the status of the mother and child will be forwarded to Alexion. Generally, the follow-up will be no longer than 3 months following the delivery date. Any termination of the pregnancy will be reported regardless of fetal status (presence or absence of anomalies) or indication for the procedure.

Female participants who become pregnant

- The Investigator will collect pregnancy information on any female participant who becomes pregnant while participating in this study. The initial information will be recorded on the appropriate form and submitted to Alexion within 24 hours of learning of a participant's pregnancy.
- The participant will be followed to determine the outcome of the pregnancy. The Investigator will collect follow-up information on the participant and the neonate, and the information will be forwarded to Alexion. Generally, follow-up will not be required for longer than 3 months beyond the delivery date. Any termination of pregnancy will be reported, regardless of fetal status (presence or absence of anomalies) or indication for the procedure.
- While pregnancy itself is not considered to be an AE or SAE, any pregnancy complication or elective termination of a pregnancy for medical reasons will be reported as an AE or SAE. A spontaneous abortion (occurring at < 22 weeks gestational age) or still birth (occurring at > 22 weeks gestational age) is always considered to be an SAE and will be reported as such. Any post-study pregnancy related SAE considered reasonably related to the study intervention by the Investigator will be reported to Alexion as described in [Section 8.3.4](#). While the Investigator is not obligated to actively seek this information in former study participants, he or she may learn of an SAE through spontaneous reporting.

